## **17.0 SPECIAL NOTES**

### **17.1 Informed Consent**

A written consent form will be obtained from each subject and filed by the Investigator with the subject's records, in accordance with 21 CFR Part 50.

### **17.2 Alteration of the Study**

Neither the Investigator, nor the Sponsor, will modify or alter this protocol without first obtaining the concurrence of the other parties. All protocol modifications including, but not limited to changes in the Principal Investigator, inclusion/exclusion criteria, number of subjects to be enrolled, study sites, or procedures must be submitted to the GIRB as a written amendment for review and approval prior to implementation, with one exception: when necessary to eliminate an apparent immediate hazard to the subject.

### **17.3 Procedures for Accounting for Missing Data**

Missing microbiological data at 30 seconds, 10 minutes, or 6 hours will be reported as missing; if the entire sample is missing the site will be treated as a nonresponder for that sample time. These subjects will be included in the mITT data set based on the criteria defined above. Details of any other missing data handling will be specified in the statistical analysis.

### **17.4 Protocol Deviations**

This study will be conducted as described in this protocol, except for an emergency situation in which the protection, safety, and well-being of the subject requires immediate interventions, based on the judgment of the Investigator. In the event of a significant deviation from the protocol due to an emergency, accident, or mistake, the Investigator or designee will document the details of the situation and any subsequent decisions. All deviations from the protocol or approved amendments shall be documented by BioScience Laboratories, Inc. Any deviation to the protocol that may have an effect on the safety or rights of the subjects must be reported immediately (within 24 hours) to the local GIRB and sponsor representative. Any deviation that may compromise the statistical analysis of the study must be reported immediately (within 24 hours) to the sponsor representative. The sponsor shall be contacted via telephone at [REDACTED]  
[REDACTED]

## **18.0 FINAL REPORT**

The final report will be generated using ICH format and will summarize the method, data, and conclusions relative to the test materials and the subjects. Copies of the data will be incorporated into the report.

## **19.0 APPROVAL OF PROTOCOL AMENDMENTS**

No changes may be implemented to any aspects of this protocol until written approval has been obtained from the Sponsor and the GIRB with one exception: when necessary to eliminate an apparent immediate hazard to the subject.

## **21.0 DOCUMENTATION AND RECORD-KEEPING**

### **21.1 Data Collection**

Any contact with subject via telephone or other means that provides significant clinical information will also be documented in the progress notes and/or BSLI forms as appropriate.

Any changes to information in the study progress notes and other source documents will be initialed and dated on the day the change is made by study personnel authorized to make the change. If the reason for the change is not apparent, a brief explanation will be written adjacent to the change.

If a subject needs to make a correction, the subject will initial and/or date the correction they make on the source document.

### **21.2 Source Document Maintenance**

Source documents are defined as the results of original observations and activities of a clinical investigation. Source documents will include, but are not limited to study progress notes, computer printouts, screening logs, laboratory notebooks and recorded data from automated instruments. All source documents produced in this study will be maintained by the Investigator and made available for inspection by authorized persons. The Case Report Forms (CRFs) will be the primary source documents for the study. All data will be directly recorded on the CRFs. The original signed informed consent form from each participating subject will be filed in the Study File and a copy given to the subject.

### **21.3 File Management at the Study Site**

The Investigator will not dispose of any records relevant to this study without written permission from the Sponsor and providing an opportunity for the Sponsor to collect such records. The Investigator shall take responsibility for maintaining adequate and accurate hard-copy source documents of all observations and data generated during this study including but not limited to the essential documents noted below in Section 21.4. Such documentation is subject to inspection by the Sponsor, the FDA, or any applicable regulatory agency. If the Investigator is not able to store the records, he or she will contact the Sponsor and make arrangements for the Sponsor to assume the responsibility for the continued storage.

### **21.4 Study File Management**

It will be the responsibility of the Investigator to assure that the Study File is maintained. The Study File for this protocol will contain, but will not be limited to, the information listed below:

- Investigational Brochure or other appropriate product safety information
- Signed Protocol
- Revised Protocol (if applicable)
- IRB-Approved Informed Consent Form (blank)
- Copy of Signed Form(s) FDA-1572
- Financial Disclosure for the Principal Investigator and Subinvestigators
- Curriculum Vitae of Principal Investigator and Subinvestigators
- DHHS Number for IRB, or other documentation of IRB compliance with FDA regulation
- Documentation of IRB approval of protocol, consent form, any protocol amendments and any consent form revisions
- All correspondence between the Investigator, IRB, and Sponsor relating to study conduct
- Copies of information related to SAE and the information on Immediately Reported Adverse Events
- Copy of completed Initiation Report
- Testing Facility Site Signature Log
- FDA's Clinical Investigator Information Sheets (if applicable)
- CRA Monitoring Log (if applicable)

- Drug Invoices
- Study specific training records for Testing Facility site personnel
- Enrollment/Disposition log showing subjects screened, enrolled, disqualified, withdrawn, and completed
- Sample Submission Form (if provided by Sponsor), Product Receipt Logs and Product Tracking Forms

To protect privacy and maintain the confidentiality of data, subjects will be assigned a unique study number, all study samples and research records will be identified using the subject's study number, and electronic databases will be kept on password-protected computers.

## **22.0 LIABILITY AND INDEMNIFICATION**

Test Facility's liability to Sponsor under this Protocol shall be limited to the price of this evaluation. Sponsor shall be responsible to Study Participants (when applicable) (including study related Adverse Events that occur as a part of testing in this study) and to other third parties for the fitness of the test materials for use as defined in the Study Protocol.

**APPENDIX 1**  
**PRODUCT APPLICATION INSTRUCTIONS**

## APPENDIX 1

[figure not shown]
### PRODUCT APPLICATION INSTRUCTIONS (Page 1 of 2)

#### **Treatment Site Application Instructions**

##### Abdominal Test Site

1)

2)

##### Inguinal Test Site

1)

2)

## APPENDIX 1

### PRODUCT APPLICATION INSTRUCTIONS (Page 2 of 2)

#### **Treatment Site Application Instructions**

##### Abdominal Test Site

##### Inguinal Test Site

[figure not shown]
**APPENDIX 2**  
**ANATOMICAL DIAGRAM OF THE SAMPLING SITES**

PROTOCOL #150316-103  
Sponsor Project Number: ZX-ZP-0074  
Page 37 of 49  
[REDACTED]  
[REDACTED]  
[REDACTED]

[figure not shown]
## APPENDIX 2

### ANATOMICAL DIAGRAM OF THE SAMPLING SITES

#### INGUINAL TEST SITES

#### ABDOMINAL TEST SITES

## **APPENDIX 3**

### **VALIDATION OF NEUTRALIZER EFFECTIVENESS**

### **APPENDIX 3**

## VALIDATION OF NEUTRALIZER EFFECTIVENESS

## 1.0 PURPOSE OF NEUTRALIZER EFFECTIVENESS STUDY

The purpose of this neutralization study is to assure that the neutralizers used in the recovery medium quench the antimicrobial activity of the test materials, and are not toxic to the bacteria. The study will comprise both an *In-Vivo* component performed using human subjects, and an *In-Vitro* component performed based on ASTM E1054-08(2013), *Standard Test Methods for Evaluation of Inactivators of Antimicrobial Agents*.

will be used as the challenge species in both components of the neutralizer validation study.

## 2.0 SCOPE

An effective nontoxic method of neutralization must be employed to eliminate the antimicrobial activity of a test material quickly. Sufficient supporting data are required to show that the neutralizing method employed is effective. A known population of microorganism must be exposed to the antimicrobial test materials, diluent/recovery media, the neutralizing solution, and the neutralizing solution plus antimicrobial test material in order to determine whether microbial inhibition is present.

Neutralizing methods include chemical inactivation, dilution of antimicrobial test material to a sub-inhibitory concentration, and membrane filtration. The procedures detailed here deal with chemical inactivation and dilution of antimicrobial test material, as well as recovery from human subjects.

The *In-Vivo* component of the neutralization study will use the two active test materials (ZuraPrep™ and ChloraPrep®) and the negative control (ZuraPrep™ Vehicle). At least [REDACTED] subjects will be tested using product applications on the skin of the abdomen, to obtain a minimum of [REDACTED] samples per test material challenged with each challenge species.

[figure not shown]
### 3.0 TEST MATERIALS

The test materials will be received and stored by BioScience Laboratories, Inc. (BSLI) in accordance with instructions from the Sponsor and retained in secure quarantine when not being used in testing. BSLI will maintain an inventory of the test materials in secure

quarantine and a log of use. Unused, sealed test materials will be stored by BSLI until the Sponsor specifies its disposition. In the absence of a disposition request from the Sponsor within 1 year of planned usage, the test materials will be returned to the Sponsor. No test materials will be destroyed unless so requested by the Sponsor. Complete product information will be provided in the Final Report, if it is not provided below, if provided by the Sponsor.

Test Product: ZuraPrep™ [REDACTED]  
Active Ingredient: Isopropyl Alcohol (~70%)  
Other Ingredients: [REDACTED]  
  
Manufacturer: [REDACTED]  
Lot Number: [REDACTED]  
Manufacture Date: [REDACTED]  
Expiration Date: [REDACTED]  
  
Positive Control: ChloraPrep® [REDACTED] (Scrub Teal® Tint)  
Active Ingredients: 2% Chlorhexidine gluconate (w/v) and 70% isopropyl alcohol (v/v)  
Lot Number: \_\_\_\_\_  
Expiration Date: \_\_\_\_\_  
  
Negative Control: ZuraPrep™ Vehicle [REDACTED]  
Other Ingredients: [REDACTED]  
  
Manufacturer: [REDACTED]  
Lot Number: [REDACTED]  
Manufacture Date: [REDACTED]  
Expiration Date: [REDACTED]

Applicators:

Lot Number:

Expiration Date:

## **4.0 LABORATORY EQUIPMENT, SUPPLIES AND MEDIA**

### **4.1 EQUIPMENT**

The equipment used during this neutralization will be detailed on Clinical Trials Equipment Tracking Form(s), and the form(s) will be included in the Final Report.

### **4.2 SUPPLIES**

The supplies used during this neutralization will be detailed on Supplies Tracking Form(s) and the form(s) will be included in the Final Report.

### **4.3 TEST MEDIA**

#### Sampling Solution

Stripping Suspending Fluid (SSF)

Stripping Suspending Fluid with product neutralizers / 10% Tween (SS+)

#### Diluting Fluid

Butterfield's Phosphate Buffer Solution with product neutralizers (PBW+)

#### Media

Tryptic Soy Agar with product neutralizers (TSA+)

Tryptic Soy Agar (TSA)

Tryptic Soy Broth (TSB)

Phosphate Buffered Saline (PBS)

## **5.0 SUBJECT SELECTION**

### **5.1 Number of Subjects**

[figure not shown]
A sufficient number of overtly healthy subjects at least 18 years of age will be admitted into the study to ensure collection of at least [REDACTED] samples for each of the three test materials and each challenge species ([REDACTED]).

### **5.2 Subject Recruitment**

Subjects must meet the inclusion and exclusion criteria in Section 11.0 of the protocol to which this neutralizer validation is attached, except for the baseline bacterial count, the 72-hour exclusion from showering/bathing criteria, and the length of the washout period. The neutralization subjects do not require a minimum baseline count and they only need to avoid topical and systemic antimicrobials for 7 days (not 14 days) prior to Test Day. Subjects will be asked to provide information on demographics and inclusion/exclusion criteria and sign the Informed Consent and Authorization Forms including Authorization to Use and Disclose Protected Health Information Form, and List of Restricted Products before beginning the 7-day washout period (subjects will be provided with a product restriction kit). When subjects return to begin their participation in the study they will again be asked to provide information relative to inclusion/exclusion criteria. If they meet all inclusion/exclusion criteria, they may be enrolled. These subjects will be identified by the letter "N" for neutralization and a subject number starting with 001.

Each subject will receive the three test materials (ZuraPrep™, ZuraPrep™ Vehicle [ZuraPrep™ without IPA], and ChloraPrep®), randomly assigned to a side of the abdomen, which will be applied to two separate 1.5" x 5" test sites on the abdomen. See diagram below.

**Neutralization Test Sites Diagram**

## **8.0 PROCEDURES**

### **8.1 Compliance with Good Clinical Practices and Regulatory Requirements**

The study will be conducted in compliance with the Good Clinical Practice regulations as required by the FDA, Good Laboratory Practice regulations as required by the FDA, the standard operating procedures of BioScience Laboratories, Inc., the study protocol, and any protocol amendments, and the regulatory requirements of the FDA and ICH.

Subjects will be questioned prior to and during the study to ensure compliance with study requirements.

### **8.2 Product-Restriction Period**

The 7-day period prior to the neutralization will be designated the "product-restriction" period. During this time, subjects will avoid the use of medicated soaps, lotions,

shampoos, deodorants (with exception of deodorant provided in the product-restriction kit), etc., as well as skin contact with solvents, acids, and bases. Subjects will also avoid sunbathing, using UV tanning beds or bathing in biocide-treated (e.g., chlorinated) pools and/or hot tubs. Subjects will be provided a kit containing products that they will be instructed to use exclusively for personal hygiene during the course of the study.

Subjects must not remove hair from the anatomical sites to be treated from the beginning of the product restriction period until after the neutralization has been completed.

During the Product-Restriction Period (at least 72 hours prior to the test period), the subjects will be examined physically to ensure that there is no evidence of injury, dermatosis, or dermatitis present at the sampling sites, and hair on sampling sites will be clipped, if needed (reference Appendix 2).

### **8.3 Randomization**

The test product (ZuraPrepTM), the positive control (ChloraPrep®) and the negative control (ZuraPrepTM Vehicle) will be assigned randomly to test sites per a computer-generated randomization schedule, such that each subject receives two of the three test materials at the abdominal sites. See diagram above.

The challenge species will not be randomly assigned to a subject. Each challenge species will be tested separately and a group of [REDACTED] will provide the samples for each challenge species.

### **8.4 Test Inoculum Preparation**

Two days prior to beginning the neutralization assay, [REDACTED]

from a stock culture

slant, lyophilized vial, or cryogenic stock culture will be transferred into a tube containing Tryptic Soy Broth (TSB). The tube will be incubated for 24 hours  $\pm$  4 hours at 30 °C  $\pm$  2 °C.

One day prior to beginning the neutralization assay, loopfuls of the broth culture will be streaked onto Tryptic Soy Agar (TSA) plates, and the plates will be incubated for 24 hours  $\pm$  4 hours at 30 °C  $\pm$  2 °C.

Immediately prior to initiating the neutralization assay, an inoculum suspension will be prepared in Phosphate Buffer Saline (PBS) solution from the culture on an agar plate, and the concentration adjusted to approximately  $3.0 \times 10^8$  to  $1.0 \times 10^9$  CFU/mL. The suspension will then be serially diluted in PBS to achieve an inoculum titer of approximately  $3.0 \times 10^3$  to  $1.0 \times 10^4$  CFU/mL, and used as test inoculum. The below procedures will be performed with both microorganisms.

### **8.5 Inoculum Assay (Initial population) – Test C**

Test Inoculum will be assayed by adding a [REDACTED] aliquot of the inoculum to [REDACTED] of Phosphate Buffer Saline (PBS) solution (IP), vortexing for at least 3 seconds, and immediately (within 1 minute) pour-plating, in duplicate, [REDACTED] aliquots of the IP with TSA. This assay will be performed five additional times for a total of six replicates.

The diluted test inoculum suspensions will be allowed to stand for at least 30 minutes, following which, [REDACTED] aliquots will be pour-plated, in duplicate, with TSA.

### **8.6 Product Efficacy Evaluation (*In Vitro*) – Test D**

This phase of the neutralization assay determines whether the antimicrobial test material is able to reduce the population of the challenge microorganism. This assay will be performed in six replicates.

To each of six test tubes containing [REDACTED] of each Test Material, a [REDACTED] aliquot of the test inoculum will be added. The suspensions will be vortexed for at least 3 seconds and, immediately (within 1 minute), [REDACTED] aliquots of each replicate will be pour-plated, in duplicate, with TSA.

The tubes will be allowed to stand for at least 30 minutes, following which [REDACTED] aliquots of each replicate will be pour-plated, in duplicate, with TSA.

### **8.7 Neutralizing/Recovery Medium Inhibition Evaluations (*In Vitro*) – Test B**

This phase of the neutralization assay assures that the sterile Stripping Suspending Fluid (SSF) and the sterile Stripping Suspending Fluid with product neutralizers (SS+), the sampling solutions employed in the evaluation, are not inherently toxic to the microorganisms. This assay will be performed in six replicates.

To each of six test tubes containing [REDACTED] of one of the sampling solutions, a [REDACTED] aliquot of the test inoculum will be added. The suspensions will be vortexed for at least 3 seconds and, immediately (within 1 minute), [REDACTED] aliquots of each replicate will be pour-plated, in duplicate, with Tryptic Soy Agar with product neutralizers (TSA+).

The tubes will be allowed to stand for at least 30 minutes, following which [REDACTED] aliquots of each replicate will be pour-plated, in duplicate, with TSA+.

This same procedure will be repeated for the remaining sampling solution

### **8.8 Diluent Broth Inhibition Evaluation (*In Vitro*) – Test B**

This phase of the neutralization assay assures that the Butterfield's Phosphate Buffer Solution with product neutralizers (PBW+) employed in the evaluation is not inherently toxic to the microorganism. This assay will be performed in six replicates.

Six test tubes containing [REDACTED] of diluent broth to be used in the test will be prepared, and a [REDACTED] aliquot of the test inoculum will be transferred to each tube. The suspension will be vortexed for at least 3 seconds, and immediately (within 1 minute), [REDACTED] aliquots of each replicate will be pour-plated, in duplicate, with TSA+.

The tubes will be allowed to stand for at least 30 minutes, following which, [REDACTED] aliquots of each replicate will be pour-plated, in duplicate, with TSA+.

### 8.9 Neutralizer Efficacy Evaluation (*In Vivo*) – Test A

This phase of the evaluation determines whether the neutralizing method chosen effectively eliminates the antimicrobial activity of the test materials contained in the applicators.

Prior to sampling, the subjects will be questioned regarding adherence to the protocol. Subjects will also be examined physically to ensure no evidence of injury, dermatosis, or dermatitis is present at the sampling sites. Female subjects will be required to provide a urine sample for a pregnancy test. Only those female subjects with a negative test will be allowed to proceed into testing.

A 1.5" x 5" test area will be demarcated on each side of the abdomen. After the test areas are marked, each area will be processed using three 70% isopropyl alcohol swabs for a total of ~ 90 seconds (~ 30 seconds each), followed by an air-dry for at least 1 minute. This step will prepare the skin for the neutralization test.

A test material (reference Section 3.0 of the Validation of Neutralizer Effectiveness) will be applied to a 1.5" x 5" site on the abdomen of the subjects following the instructions for inguinal application in Appendix 1, with the randomly assigned test material.

The site will then be sampled using the Cylinder Sampling (Scrub Cup) Technique 30 ± 5 seconds post product-application completion.

The Cylinder Sampling (Scrub Cup) Technique will be performed as described in Section 13.6 of the Study Protocol (using SS+).

The volume of sample will be adjusted to [REDACTED] inoculated with [REDACTED] of the test inoculum, and vortexed for at least 3 seconds. Immediately (within approximately 1 minute), [REDACTED] aliquots will be pour-plated, in duplicate, with TSA+.

The tube containing the sample and inocula will be allowed to stand for at least 30 minutes. Following the exposure, [REDACTED] aliquots of each sample will be pour-plated, in duplicate, with TSA+.

The process will be repeated on the remaining abdominal site with the randomly assigned test material. A total of nine subjects will be treated on the both sides of the abdomen with two of the three test material and for each challenge species. A total of [REDACTED] will be treated with two of the three test materials (samples from [REDACTED] used for

one microorganism, samples from the remaining nine subjects used for the remaining microorganism).

Following all sampling, each test site will be cleaned using a towelette saturated with tap water and/or mild soap to remove the test material from the skin.

#### **8.10 Incubation**

The inoculated plates will be incubated at  $30^{\circ}\text{C} \pm 2^{\circ}\text{C}$  for approximately 72 hours, or until sufficient growth is visible.

#### **9.0 CALCULATIONS**

**9.1** The following formula will be used to calculate the number of viable bacteria recovered:

$$\text{Log}_{10} \left\{ \frac{A + B}{2} \right\}$$

Where:

A and B = Individual Plate Counts

**9.2** If colonies on one of the plates are uncountable, the count from the remaining plate will be used.

#### **10.0 STATISTICS**

**10.1** After calculating the  $\text{log}_{10}$  populations recovered from Tests D, B, and A, these will be statistically compared to the Initial Population (Control) using a One-Way Analysis of Variance (ANOVA) with Dunnett Multiple Comparisons with the Control. All statistical calculations will be performed using the 0.05 level of significance for Type I ( $\alpha$ ) error.

**10.2** Prior to comparing Phases to the Initial Population (Control), the 30-minute evaluation of the Initial Population should be shown to be statistically equivalent to the “time-zero” Initial Population of the microorganism. Hypotheses are:

$H_0$  : Initial Population = Test Phase, or

$H_A$  : Initial Population  $\neq$  Test Phase.

If  $p \leq 0.05$  for each comparison to the control,  $H_0$  will be rejected and the Test Phase will be considered to be significantly different from the Initial Population. There is potential for low variance of the data, which would result in rejecting  $H_0$ . The difference between the Initial Population and the Test Phase will also be used to confirm significant differences. If the difference is greater than or equal to 0.20, the two tests will be determined to be significantly different. Differences less than 0.20 between the two tests will be determined to be not different.

**10.3** The Product Efficacy evaluation is effective if the antimicrobial test product produces a significant reduction in the population of the microorganism.

- 10.4** The Neutralizing/Recovery Medium Inhibition Evaluations are considered non-inhibitory if all recovered populations are not statistically different from the Initial Population of the microorganism.
- 10.5** The Diluent Broth Inhibition Evaluation is considered non-inhibitory if all recovered populations are not statistically different from the Initial Population of the microorganism.
- 10.6** Neutralization is considered adequate if all recovery populations are not statistically different from the Initial Population.

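### Appendix 3 treats non-significance as proof of neutralization and does not settle how the p-value and its 0.20 log10 rule combine, so a loss of 0.20 or more can both pass and fail

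*Combined protocol and SAP*

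**What the plan says.** Appendix 3 compares recovered populations with the Initial Population (Test C). By Section 10.1 the "populations recovered from Tests D, B, and A" enter the comparison, and "these will be statistically compared to the Initial Population (Control) using a One-Way Analysis of Variance (ANOVA) with Dunnett Multiple Comparisons with the Control". The level is fixed: "All statistical calculations will be performed using the 0.05 level of significance for Type I" error. The null hypothesis in Section 10.2 is equality and the alternative is two-sided.

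Section 10.6 gives the acceptance rule for Test A, the in-vivo neutralizer test: "Neutralization is considered adequate if all recovery populations are not statistically different from the Initial Population". Sections 10.4 and 10.5 use the same form for the sampling fluids and the diluent (Test B).

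Section 10.2 first says that p ≤ 0.05 means different. It then notes that low variance could cause rejection, and says the size of the difference will also serve to confirm significant differences. It ends with two sentences. One covers larger differences: "If the difference is greater than or equal to 0.20, the two tests will be determined to be significantly different". The other, which closes the section, covers smaller ones: "Differences less than 0.20 between the two tests will be determined to be not different".

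On sample size, Section 8.9 says: "A total of nine subjects will be treated on the both sides of the abdomen with two of the three test material", for each challenge species. The printed sample counts are redacted.

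**The concern.** A test of equality that does not reject is weak evidence of equality, and weaker still when data are few and noisy. Under Sections 10.4 to 10.6 more noise makes a pass easier. The 0.20 rule could cure this, but Section 10.2 introduces it as a confirmation of significant results. That suggests it was meant to excuse trivial differences, not to catch large non-significant ones. The closing sentences read the other way, as a rule that decides by itself. A loss of 0.25 with p > 0.05 therefore has two verdicts.

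Baseline samples are taken before any product is applied (Sections 13.5 and 13.6). Residual activity in the tube or plate would therefore lower only the post-application counts of the material that is poorly neutralized. That would raise its log reductions and its responder rates. If the loss differs between materials, it would also bias the ATE comparisons added by the amendment of 08/29/2017: the 0.5 non-inferiority margin against ChloraPrep and the 1.2 superiority margin against vehicle. A loss of 0.20 in one product only, carried over in full, is 0.20 / 0.5 = 40% of the non-inferiority margin.

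**Working it through.** The plan gives no SD, power or sample-size figure for the neutralizer study, so there is no stated figure to reproduce.

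**Inputs**
- Test A samples per material and species: 9 subjects × 2 sites / 3 materials = 6 (Section 8.9; Section 8.3 also says two of three materials per subject). Section 5.2 says that each subject receives all three materials on two sites. The passages must be reconciled; 6 rests on 8.3 and 8.9.
- Tests C, B and D: six replicates each (Sections 8.5 to 8.8).
- Level 0.05, two-sided, Dunnett (Sections 10.1 and 10.2).
- Assumed: replicate SD 0.10 to 0.25 log10, and one analysis per species and time point.

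**Standard error of a difference:** SE = SD × √(2/6).

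**Reading 1, the p-value decides.** Comparing 3 fluids (Test B) and 3 materials (Test A) with the control gives 6 comparisons and 7 × 6 − 7 = 35 df. The simulated Dunnett critical value is about 2.70. The smallest difference that can be flagged is 2.70 × SE. Pass rates are simulated.

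**Reading 2, the 0.20 rule decides.** For a true loss of 0.30, pass probability = Φ((0.20 − 0.30) / SE).

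| SD | SE | Smallest flagged | 0.30 loss passes on p | 0.30 loss passes on 0.20 rule | Observed loss ≥ 0.20 but p > 0.05 |
|---|---|---|---|---|---|
| 0.10 | 0.058 | 0.16 | 1% | 4% | 0% |
| 0.15 | 0.087 | 0.23 | 23% | 12% | 11% |
| 0.20 | 0.115 | 0.31 | 53% | 19% | 34% |
| 0.25 | 0.144 | 0.39 | 72% | 24% | 47% |

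The last column is how often the two sentences of the plan conflict in this direction when the true loss is 0.30. At SD 0.10 it does not arise, because Dunnett flags differences below 0.20.

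For a true loss of exactly 0.20, the rule passes Φ(0) = 50% at any SD, because it uses the point difference without a bound.

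**All populations must pass.** If the 0.30 loss is present in both species, the rates multiply. On p at SD 0.15, 0.20 and 0.25: 0.23² = 5%, 0.53² = 28%, 0.72² = 52%. On the 0.20 rule: 0.12² = 1%, 0.19² = 4%, 0.24² = 6%. Testing at both 0 and 30 minutes lowers them further. A loss confined to one species gets no such reduction.

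**Test D in the same ANOVA.** This would give 9 comparisons, 10 × 6 − 10 = 50 df and a critical value of about 2.79. With the other groups at SD 0.15, the pooled SD is √((35 × 0.15² + 15 × SD_D²) / 50).

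| Test D SD (assumed) | Pooled SD | 0.30 loss passes on p |
|---|---|---|
| 0 (uniform kill) | 0.125 | 13% |
| 0.15 | 0.150 | 25% |
| 0.5 (partial, noisy kill) | 0.301 | about 94% |

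Test D can move the Test A verdict either way. Under reading 2 it has no effect.

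**The case against.** The strongest reply is that the closing sentences of Section 10.2 already define what counts as different. Read literally, an observed loss of 0.25 fails, and the first change below restates existing text. A loss of 0.50 would then pass at most about 4% of the time for SDs from 0.10 to 0.30. This stands as a reading. It is not the only one, because the sentence introducing the rule gives it a confirming role and Section 10.6 speaks only of statistical difference.

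Second, Section 10.2 itself expects low variance, and at SD 0.10 a 0.30 loss passes on p alone only about 1% of the time. This also stands: the size of the problem depends on an SD that the documents do not give.

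Third, the tabulated rates are for one comparison, whereas Section 10.6 requires all populations to pass. That is correct when the loss is shared across species or times.

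Fourth, Section 10.1 does not say how many ANOVAs are run. A shared error term with Test D is the natural reading of a one-way ANOVA on D, B and A, but it is an inference.

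Finally, neutralizers are in the post-application sampling fluid, the diluent and the agar, and dilution and plating finish within 30 minutes (Sections 13.6 and 13.7), which matches the validation's minimum hold. This limits the opportunity for carry-over. Whether those neutralizers work is, however, what Appendix 3 is meant to show.

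**Conclusion.** The point holds as a defect in the acceptance rule. Non-significance with about 6 samples is used as proof, and the plan gives opposite verdicts when the loss is 0.20 or more and p > 0.05. A true 0.30 loss passes one comparison 1% to 72% of the time on p alone and 4% to 24% on the 0.20 rule, across SDs of 0.10 to 0.25. These figures rest on the assumed SDs, normal errors, 6 samples per group and a single comparison.

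Three stronger readings are tempting and not supported. A reader might infer that the plan has no safeguard beyond a p-value; the 0.20 sentences are there, and if they decide, large losses rarely pass. A reader might infer that including Test D makes the test lax; the direction depends on Test D's spread, and the pooling is not stated. A reader might infer that every log reduction is inflated; carry-over is specific to a material and to post-application counts, and nothing in the documents shows that any occurred. No effect on responder rates or ATE estimates has been calculated here.

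**What to change.** In Appendix 3, Section 10:

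1. State that a mean loss against the Initial Population of 0.20 log10 or more means inadequate neutralization (or an inhibitory medium or diluent), whatever the p-value.
2. Compare Test D with the Initial Population separately, and leave it out of the error term for Tests A and B.
3. Report the one-sided 95% upper bound of the Test A loss for each material, species and time, without making it pass/fail.

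The bound should be descriptive because, as a criterion, it would fail sound neutralizers. With no true loss it falls below 0.20 in about 96%, 73%, 52% and 39% of single comparisons at SD 0.10, 0.15, 0.20 and 0.25. Testing was complete by the 08/29/2017 amendment, so a new criterion would also be post hoc.

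Cost: wording and a re-run of existing calculations; no new samples. Under change 1 a noisy but sound neutralizer fails somewhat more often. With no true loss, differences of 0.20 or more in either direction occur in 2 × (1 − Φ(0.20 / 0.087)) = about 2% of comparisons at SD 0.15 and 2 × (1 − Φ(0.20 / 0.115)) = about 8% at SD 0.20, against about 1% failing on p alone. Counting losses only, as change 1 is worded, halves these to about 1% and 4%.
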